8.3.3. Week 2 Visit – Youth Friendship Bench SA participants only

- 1. Only participants randomized to the Youth Friendship Bench SA intervention will complete this visit, which will be their 2nd counseling session. This session may be conducted via phone.
- Schedule participant for their Week 4 visit in 14 days. The Week 4 visit will be scheduled as an in-person session for a time when they are able to return to the clinic.

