8.3.5. Week 8 Visit – Youth Friendship Bench SA participants only

- Participants randomized to the Youth Friendship Bench SA intervention will complete their 4th counseling session at this visit. This session may be conducted via phone
- 2. Schedule participant for their Week 12 visit in 30 days.
- Schedule participants for optional group session (either in person or via WhatsApp as they
 prefer, for between the Week 8 and 12 visits with the exact timing depending on availability of
 participants and enrollment accrual rates).

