8.3.7. Interim Contacts and Visits

Interim contacts and visits (those between regularly scheduled follow up visits) may be performed at participant request or as deemed necessary by the clinic staff. We will ask participants about whether they attended the clinic for an interim visit at each study vist and will inquire about interim visit reason and outcome.

Some interim visits may occur for administrative reasons. For example, the participant may have questions for study staff. Other interim contacts and visits may occur in response to AEs experienced by study participants. When interim contacts or visits are completed in response to participant reports of AEs, study staff will assess the reported event clinically, record the event on the CRF, and provide or refer the participant to appropriate medical care.

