9.3. Adverse Event Definition and Reporting

For the purposes of this study, only serious adverse events (SAEs) and adverse events of special interest (AESIs) will be recorded. These will be summarized by arm, as a secondary outcome of our study. SAEs are defined as those events that result in death, are life-threatening, require inpatient hospitalization or prolongation of existing hospitalization, and/or result in persistent or significant disability/incapacity. AESIs are considered reports of self-harm or self-injury.

With appropriate permission of the participant, whenever possible, records from all non-study medical providers related to SAEs will be obtained and required data elements will be recorded

on study CRFs. All participants reporting an AE will be followed clinically, until the AE resolves (returns to baseline) or stabilizes.

Site staff will also report information regarding SAEs to their IRB or other local regulatory agencies in accordance with all applicable regulations and local IRB requirements.

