11.0 STATISTICAL CONSIDERATIONS

11.1. Review of Study Design

At enrollment, women will be randomized 1:1 to either the standard-of-care mental health services (screening, referral, etc.) plus the Youth Friendship Bench SA intervention or standard-of-care services alone. Participants receiving the Youth Friendship Bench SA will complete individual counseling sessions at Enrollment, Week 2 (option to be conducted remotely), Week 4, Week 8 (option to be conducted remotely), and Week 12. They will also be invited to participate in an in-person or virtual group-based session (between their Week 8 and 12 visits, with the exact timing depending on participant availability and participant accrual rate) focused on an economic empowerment activity like job and school applications. Participants in the standard-of-care arm will complete visits at Enrollment, Week 4, and Week 12. The co-primary outcomes are: 1) the proportion with PrEP adherence measured by TFV levels detected in urine using a POC assay at Week 12 and 2) the proportion with reduced symptoms of common mental disorders measured by the SRQ-20 at Week 12. For the PrEP adherence measure, we will utilize urine TFV levels to assess PrEP dosing in the prior 4-7 days. The assay uses a threshold

of 1500 ng/mL to categorize participants as adherent as this was associated with daily dosing over 4-7 days in directly observed therapy.¹¹²

We will conduct all randomizations using a SAS-based computer-generated randomization scheme developed by the study data manager. The site sub-investigator will conduct the randomizations and fill out a randomization log which will be reviewed by the study data manager during visits to the study site. The identity of participants in each of the arms will not be known to investigators and access to the randomization code will be strictly controlled. The study blind will be broken only on completion of the clinical study and after the database has been locked. The study investigators will receive the unblended results only after that point.

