Appendix 4: Schedule of Study Visits and Procedures

	ENROLLMENT	WEEK 2	WEEK 4	WEEK 8	WEEK 12			
Administrative and Behavioral Evaluations/Procedures								
Informed Consent	X							
Collect/update locator information	X		x					
Apply inclusion/exclusion criteria, including the SRQ-20	X							
Randomization	X							
Collect demographics, behavioral, and psychosocial data, including the SRQ-20	X		x		Х			
PrEP adherence assessment via self-report			x		X			
Youth Friendship Bench SA counseling	X	X1	x	X1	Х			
Standard-of-care mental health service delivery	X		x		Х			
Assess any SAEs		x	x	X	X			
Laboratory Evaluation/Procedures								
Urine sample collection for TFV testing using a point-of-care assay			X		X			
PrEP counseling based on urine TFV drug levels			x		Х			

TFV=tenofovir; PrEP=pre-exposure prophylaxis; SAE=serious adverse event; SRQ-20=self-reporting questionnaire 20-item ¹Youth Friendship Bench SA sessions could be conducted remotely via phone

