- SAEs (including events that result in death, are life-threatening, require inpatient hospitalization or prolongation of existing hospitalization, and/or result in persistent or significant disability/incapacity) and adverse events of special interest (reports of self-harm or self-injury).
- We will analyze qualitative data (in-depth interviews, clinic observation field notes) using an inductive and deductive coding approach and will use descriptive statistics to summarize quantitative data on intervention acceptability, feasibility, and appropriateness and SAEs and AESIs.

Secondary Analysis 5: To monitor and describe the occurrence of serious adverse events over the study (defined as those events that result in death, are life-threatening, require inpatient hospitalization or prolongation of existing hospitalization, and/or result in persistent or significant disability/incapacity) plus adverse events of special interest (reports of self-harm or self-injury).

Statistical analyses:

1) We will compute descriptive statistics to describe the occurrence of serious adverse events and adverse events of special interest. For the full study population, we will compute means, standard deviations, medians, and inter-quartile ranges for each of the adverse events that may occur. Chi-squared tests will be used to assess differences in adverse study events across meaningful groupings, such as between study arms.

Exploratory Objective 1: To explore mediators and moderators of the Youth Friendship Bench SA intervention effect on PrEP adherence.

- Mediators and moderators of the Youth Friendship Bench SA intervention effect on PrEP adherence at 12 weeks
- Covariate characteristics assessed at baseline and follow-up may include Sociodemographic characteristics; sexual behaviors; gender-based violence (GBV); symptoms of common mental disorders; self-esteem; intervention acceptability, feasibility, and appropriateness; and level of engagement with the intervention.

Exploratory Objective 2: To explore mediators and moderators of the Youth Friendship Bench SA intervention effect on symptoms of common mental disorders.

• Mediators and moderators of the Youth Friendship Bench SA intervention effect on symptoms of common mental disorders at 12 weeks

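### Secondary Analysis 5 tests adverse events between arms although scheduled SAE enquiry is four visits in the intervention arm and two in standard of care, and its summaries do not suit rare yes/no events

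*SAP*

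**What the plan says.** SAP, Secondary Analysis 5, covers SAEs plus adverse events of special interest (AESIs, meaning reports of self-harm or self-injury). It plans means, standard deviations, medians and interquartile ranges for the full study population, and then a test: "Chi-squared tests will be used to assess differences in adverse study events across meaningful groupings, such as between study arms". The SAP appendix has no table shell for adverse events. Protocol 9.3 makes the by-arm summary of these events a secondary outcome.

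Protocol Appendix 4 has a row "Assess any SAEs", marked at Weeks 2, 4, 8 and 12 and not at Enrollment. On who attends those visits:

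- Week 2 (8.3.3): "Only participants randomized to the Youth Friendship Bench SA intervention will complete this visit, which will be their 2nd counseling session".
- Week 8 (8.3.5): "Participants randomized to the Youth Friendship Bench SA intervention will complete their 4th counseling session at this visit".
- SOC (11.1): "Participants in the standard-of-care arm will complete visits at Enrollment, Week 4, and Week 12".

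Section 8.3.7 adds: "We will ask participants about whether they attended the clinic for an interim visit at each study vist". Section 8.4 limits missed-visit tracing and SMS reminders to the intervention arm, and 8.3.2 gives SOC women neither reminders nor remote services.

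**The concern.** A between-arm comparison of recorded events is fair only if events are looked for equally in both arms. Here the intervention arm is asked twice as often by schedule. The interim-visit question follows the same visits, so it is asked more often there too. With equal true risk, any incomplete recall or disclosure puts more events on record in the intervention arm.

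Self-harm under lay counseling is the signal that a safety reader would look at first. A modest excess there could not be separated cleanly from more contact, and a modest true reduction could be masked. Neither document equalizes the enquiry, limits the comparison to common visits or names the difference as a limitation. Describing retention and missingness does not help, because an SOC woman has no Week 2 or Week 8 visit to be counted as missing.

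The planned summaries are a second weakness. For an event that affects fewer than 25% of women, the median and interquartile range are 0 (0 to 0) whatever happens.

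**Working it through.** **Count.** Scheduled SAE enquiries per woman (Appendix 4 marks, limited to the visits each arm attends):

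- Intervention: Weeks 2, 4, 8, 12 = 4. SOC: Weeks 4, 12 = 2.
- With 110 randomized 1:1 (protocol 11.3), 55 per arm: 55 × 4 = 220 against 55 × 2 = 110.

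The plan gives no figure of its own to reproduce.

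**Illustrative size.** None of the following assumptions is in the documents: equal true risk; one event per affected woman, at a uniform time over 12 weeks; full attendance; each later scheduled enquiry, looking back to enrollment, reveals the event with probability q, independently of the other enquiries. Then the share of events recorded is:

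- Intervention = [2(1−(1−q)⁴) + 2(1−(1−q)³) + 4(1−(1−q)²) + 4q] / 12
- SOC = [4(1−(1−q)²) + 8q] / 12

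| q | Intervention | SOC | Ratio |
|---|---|---|---|
| 0.3 | 50.6% | 37.0% | 1.37 |
| 0.5 | 71.9% | 58.3% | 1.23 |
| 0.7 | 86.4% | 77.0% | 1.12 |
| 0.9 | 96.3% | 93.0% | 1.04 |
| 1.0 | 100% | 100% | 1.00 |

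At q = 0.5 a true risk ratio of 0.583 / 0.719 = 0.81 would read as 1.0.

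**Relaxing independence.** Suppose that q varies between women (beta-distributed, mean 0.5), so that a woman who withholds once tends to withhold again. The ratio falls from 1.23 to 1.18 at a within-woman correlation of 0.25, 1.13 at 0.5 and 1.07 at 0.75. It is 1.00 if women either always or never disclose. These correlations are also assumptions.

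**Effect on the test.** Take 55 per arm, an assumed 10% true risk and q = 0.5 with independence. Expected recorded counts are 55 × 0.10 × 0.719 = 3.95 against 55 × 0.10 × 0.583 = 3.21, a gap of about 0.7 events. By full enumeration of the uncorrected chi-squared test:

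- The intervention arm shows more events in 54% of trials and fewer in 31%.
- Two-sided rejection at 0.05 is 5.5%, against 4.6% with both arms at the SOC recording rate.
- The harm tail alone is 4.3% against 2.3%. At an assumed 2% true risk it is 0.4%.

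**After the fix.** On the common assessments the schedule is 2 against 2, so the model's ratio is 1.00 by construction.

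**The case against.** The strongest reply is that the tilt is small where the schedule applies and unproven where it might be large. Four parts of it stand.

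- Weeks 4 and 12 look back in both arms, and death or hospitalization is hard to miss. 9.3 also seeks outside medical records for SAEs.
- A reader might infer that self-harm is asked about four times against two. The documents do not support that. The Appendix 4 row names SAEs only, and no self-harm question is scheduled at Weeks 2 or 8. SRQ-20 item 17 and its suicide follow-up questions run at Weeks 4 and 12 in both arms (protocol 9.1, Mental health symptoms; Appendix 2). That screen is not complete: the follow-ups depend on item 17 being endorsed, and one asks about lifetime attempts with no since-last-visit window. Counseling sessions remain extra opportunities to disclose, but that is an inference.
- The modelled ratios depend on independent enquiries and shrink when disclosure is a trait.
- The objective is to monitor and describe, and women reporting suicidal intent or self-harm are excluded at entry (7.3.3), so counts may be very small.

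A reader might also infer that the set of events to be tested is undefined, because 8.3.7 says of an adverse event prompting an interim visit that "study staff will assess the reported event clinically, record the event on the CRF", with no seriousness limit. That does not hold. Secondary Analysis 5 names SAEs plus AESIs, and 9.3 says: "For the purposes of this study, only serious adverse events (SAEs) and adverse events of special interest (AESIs) will be recorded".

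The reply does not remove the point. The visit text in 8.3.6 lists SAE recording only at Week 12, but 8.3 calls that text additional to Appendix 4, so the 4-against-2 schedule stands and the test ignores it.

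**Conclusion.** The concern holds as a limited defect in a secondary safety analysis. The unequal schedule and the unadjusted between-arm test are plain from the documents, and the direction is toward more recorded events in the intervention arm. The size rests on assumptions: about 1.04 for well-recalled SAEs (q = 0.9), and for self-harm anything from 1.0 to about 1.2 at q = 0.5, depending on how stable disclosure is within a woman. A lower q would give more (1.37 at q = 0.3 with independence).

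A reader might conclude that the test's false-positive rate is badly inflated. It is not: two-sided error moves by about one percentage point in the 10% scenario. The difficulty is interpretive, since a small excess or reduction cannot be attributed to the intervention. The means and medians are uninformative whatever the size of the tilt. The co-primary estimates do not change.

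**What to change.** Amend Secondary Analysis 5 as follows.

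1. Record, for each event, the visit and route by which it was first learned.
2. Report all SAEs and AESIs by arm as n (%) of women with at least one event, number of events, number of women assessed per arm and visit, and risk difference with an exact 95% CI. This replaces the means, medians and chi-squared test.
3. Beside that table, give a comparison limited to events learned at the common Week 4 and Week 12 assessments or reported again there, plus all deaths and record-confirmed SAEs whenever learned. Count a woman withdrawn early because of an event as having it. Using the Week 4 and 12 answers alone would be wrong: it would drop deaths, and it would drop an intervention woman withdrawn after disclosing at Week 2 while keeping an SOC woman who discloses at Week 4.
4. List events learned only at Weeks 2 or 8 or in counseling separately by arm, untested, and state the unequal schedule as a limitation.

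The cost is one CRF field, which may need ethics approval, and one extra table. Differences in attendance and in rapport with the counselor remain; the change deals only with the schedule. Adding SAE calls to SOC women at Weeks 2 and 8 would also equalize enquiry, but it introduces remote contact that the design withholds from that arm.

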Appendix – Table shells for primary and secondary analyses

Table 1: Co-Primary Analysis 1

Associations between Youth Friendship Bench SA intervention and PrEP adherence at Week 12, assessed via univariate and multivariable Poisson regression models with robust standard errors

Exposure group	Urine TFV ≥1500 ng/mL						
	ITT analysis (n = XX)			Per-protocol analysis (n = XX)			
	n (%)	RR (95% CI)	p -value	n (%)	aRR (95% CI)	p -value	
Intervention arm							

Standard-of-care

Table 2: Co-Primary Analysis 2

Associations between Youth Friendship Bench SA intervention and symptoms of common mental health disorders at Week 12, assessed via univariate and multivariable Poisson regression models with robust standard errors

Exposure group	SRQ-20 score < 7						
	ITT analysis (n = XX)			Per-protocol analysis (n = XX)			
	n (%)	RR (95% CI)	p-value	n (%)	aRR (95% CI)	p -value	
Intervention arm							

Standard-of-care

Table 3: Secondary Analysis 1

Associations between Youth Friendship Bench SA intervention and PrEP adherence at Week 4, assessed via univariate and multivariable Poisson regression models with robust standard errors

	Urine TFV ≥1500 ng/mL						
Exposure group	ITT analysis (n = XX)			Per-protocol analysis (n = XX)			
	n (%)	RR (95% CI)	p -value	n (%)	aRR (95% CI)	p -value	
Intervention arm							
Standard-of-care							

Table 4: Secondary Analysis 2

Correlates of PrEP adherence at Week 12 assessed via univariate and multivariable logistic regression models

Characteristic	Unadjusted model		Adjusted for study arm		
	OR (95% CI)	p -value	aOR (95% CI)	p -value	
Sexual behaviors					
Gender-based violence					
Symptoms of common mental disorders					
Self-esteem					
Level of engagement with intervention					

Table 5: Secondary Analysis 3

Correlates of symptoms of common mental health disorders at Week 12 assessed via univariate and multivariable logistic regression models

Characteristic	Unadjusted model		Adjusted for study arm		
	OR (95% CI) p -value		aOR (95% CI)	p -value	
Sexual behaviors					
Gender-based violence					
Symptoms of common mental disorders					
Self-esteem					
Level of engagement with intervention					

References

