8.3.4. Week 4 Visit

- 1. Confirm consent
- 2. Confirm locator information and update as needed
- 3. Collect psychosocial and behavioral data additional data (see Section 6).
- 4. Assess symptoms of common mental disorders
 - a. All participants will receive assessments per APC guidelines and referrals as needed. They will also complete the SRQ-20 with the lay counselor.
 - b. Participants Youth Friendship Bench SA arm will complete their 3rd counseling session.
- 5. Schedule participant's next visit
 - a. Standard-of-care participants will be scheduled for their Week 12 visit in 60 days.
 - b. Youth Friendship Bench SA participants will be scheduled for their Week 8 visit in 30 days. They will be offered the option to complete the Week 8 visit in-person or remotely (over the phone).
- 6. All participants will be asked to provide a urine sample for the tenofovir (TFV) point-of-care (POC) assay. Urine POC assay testing and drug-level feedback counseling based on assay results will be conducted by the lay Youth Friendship Bench SA for participants in both arms and proceed as described in Section 5.1.2. The urine assay results will be used for research purposes only and will not be included in the clinic record.
- 7. Schedule in-depth interviews for AGYW between the Week 4 and Week 12 study visit.

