Youth Friendship Bench SA + Standard-of-Care: The Youth Friendship Bench SA intervention includes: five individual counseling sessions conducted at Enrollment, Week 2, Week 4, Week 8, and Week 12; one optional in-person or WhatsApp-based group counseling session between Week 8 and Week 12; optional remote counseling sessions; and optional one-way SMS messages to provide reminders about upcoming visits. Individual counseling sessions will last up to 60 minutes. Group counseling sessions will last up to 120 minutes. A subset of up to 30 AGYW will also be recruited to participate in gualitative in-depth interviews to be conducted between Weeks 4 and 12 of study participation. These interviews will explore their perceptions of the acceptability, feasibility, and appropriateness of the Youth Friendship Bench SA and standard-ofcare services. We will also ask about perceptions around the use of a urine POC assay for PrEP adherence assessment and drug-level feedback counseling. Throughout the study period (up to 2times per month), trained social scientist interviewers will observe participants' waiting room discussions and comfort in the clinic, clinic flow, and the clinic environment for AGYW. They will record field notes during these observations to capture key information and inform future Youth Friendship Bench SA and standard-of-care mental health service delivery. Screening data will be reviewed to determine participant eligibility. Participants who meet all inclusion criteria and none of the exclusion criteria will be entered into the study. The total duration of participant participation will be three months. We will escalate any participants who report self-harm, worsening symptoms of common mental disorders or psychiatric distress, and/or new presentation of somatic symptoms for referral and linkage to additional psychotherapy or pharmacotherapy as needed. The total duration of the study is expected to be three years.

Schema

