Analysis population: South African AGYW participants enrolled and randomized in a 1:1 ratio to either the Youth Friendship Bench SA plus SOC intervention or the SOC services alone arm.

- For an intent-to-treat analysis, we will include all randomized participants.
- For a per protocol analysis, we will include all randomized participants who received a full dose of the Youth Friendship Bench SA plus SOC intervention or SOC services alone, as specified below.

Outcome: proportion of AGYW with PrEP adherence at Week 12, defined as tenofovir (TFV) concentrations ≥1500 ng/mL in urine measured using a urine POC assay.

• We will utilize urine TFV levels to assess PrEP dosing in the prior 4-7 days.

Predictor(s) of interest: Randomized intervention arm, either the Youth Friendship Bench SA plus SOC or SOC services alone groups.

Covariate(s) of interest: For the per protocol analysis, the regression model will adjust for potential confounding from covariate characteristics assessed at baseline and follow-up, which may include:

• Sociodemographic characteristics; sexual behaviors; gender-based violence (GBV); symptoms of common mental disorders; self-esteem; and level of engagement with the intervention.

Measures of intervention use for per protocol analysis:

- Received the Youth Friendship Bench SA plus SOC intervention: 1 = received 4-5 sessions of the intervention (not including the group session). 0 = received less than 4 sessions of the intervention
- Received SOC services alone: 1 = received 4-5 sessions of SOC services alone. 0 = received less than 4 sessions of SOC services alone.

Statistical analyses:

- 1) We will compute descriptive statistics to describe the full study population of randomized individuals at baseline and to describe retention over time in both arms of the intervention. We will also summarize reasons for discontinuing PrEP.
- 2) We will compute descriptive statistics for missing data, including the pattern of missingness across visits for both arms of the intervention, and factors associated with missingness. All information from participants with missing data will be examined to determine if any pattern is evident that would account for the missingness.

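### SAP Table 3 has a per-protocol adjusted RR for Week 4 adherence that the text does not plan and that the only full-dose rule cannot support at Week 4

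*SAP*

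**What the plan says.** **The shell.** SAP Appendix, Table 3 (Secondary Analysis 1) is titled "Associations between Youth Friendship Bench SA intervention and PrEP adherence at Week 4, assessed via univariate and multivariable Poisson regression models", with robust standard errors. Beside the ITT block it has a second block, "Per-protocol analysis (n = XX", with an aRR, confidence interval and p-value.

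**The text.** SAP, Secondary Analysis 1, describes one comparative model for Week 4: an ITT Poisson regression in which randomized arm is the sole predictor. It names no per-protocol set, no dose rule and no adjustment covariates. Co-Primary Analyses 1 and 2 and Secondary Analyses 2 and 3 each state a per-protocol analysis.

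**The only full-dose rule.** Under Co-Primary Analysis 1 the SAP says of the per-protocol set that "we will include all randomized participants who received a full dose of the Youth Friendship Bench SA plus SOC intervention or SOC services alone". The measures of intervention use then define a full dose in the intervention arm as "1 = received 4-5 sessions of the intervention (not including the group session") and in the standard-of-care (SOC) arm as "1 = received 4-5 sessions of SOC services alone".

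**The schedule.** The SAP's Study Design section lists "five individual counseling sessions conducted at Enrollment, Week 2, Week 4, Week 8, and Week 12". Protocol 8.3.4 (Week 4) says "Participants Youth Friendship Bench SA arm will complete their 3rd counseling session"; Protocol 8.3.5 (Week 8) says participants "will complete their 4th counseling session at this visit". Protocol 11.1 gives SOC participants visits at Enrollment, Week 4 and Week 12 only.

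**The concern.** A per-protocol set for a Week 4 outcome should be fixed by what happened up to Week 4. Under the only rule in the SAP it cannot be, because the fourth session is at Week 8 at the earliest. An intervention participant therefore enters the set through what she does after the outcome is known.

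She also knows the outcome. Under Protocol 8.3.4 and 9.1.2 the urine result is discussed with her at the Week 4 visit, and a negative result leads to a question about whether she still wants PrEP. Her later attendance may depend on that result. Covariate adjustment does not reliably repair selection on a possible consequence of the outcome, and the Secondary Analysis 1 text names no covariates anyway.

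At stake is a reported effect estimate with a p-value for a secondary endpoint. Whoever fills the shell must either apply the four-to-five-session rule or devise another one, possibly after seeing the data.

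**Working it through.** **1. Sessions available by Week 4**

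- Intervention arm (SAP Study Design; Protocol 8.3.4 and 8.3.5): Enrollment, Week 2 and Week 4 make 3; Weeks 8 and 12 add 2; total 5. This agrees with the five sessions the SAP states.
- SOC arm (Protocol 11.1): Enrollment and Week 4 make 2; Week 12 adds 1; total 3.

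**2. Who can meet the rule**

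- Intervention arm: there are 2^5 = 32 attendance patterns. Those with at least four sessions number C(5,4) + C(5,5) = 5 + 1 = 6.
- Four of the six include both Week 8 and Week 12: all five sessions attended, or only Enrollment, Week 2 or Week 4 missed. The other two miss one of Weeks 8 and 12 and include the other. None of the six lies wholly within Week 4.
- The group session does not help. The rule excludes it, and it falls between Weeks 8 and 12.
- SOC arm, counting study visits as sessions: 2^3 = 8 patterns with a maximum of three visits, so 0 of 8 qualify.

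**3. What selection after the outcome can do (illustration only)**

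Let p be the share adherent at Week 4, and a and b the shares of adherent and non-adherent intervention women who go on to qualify. The adherent share in the selected group is

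p·a / (p·a + (1 − p)·b).

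Assumptions: no true effect; p = 0.40 in both arms (the SAP's planning value for SOC adherence, carried over to Week 4); and SOC left unrestricted, so that RR = selected share / 0.40. The values of a and b are assumed, because the documents give none.

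| a | b | Selected share | RR when the truth is 1.00 |
|---|---|---|---|
| 0.90 | 0.90 | 0.36/0.90 = 40.0% | 1.00 |
| 0.90 | 0.80 | 0.36/0.84 = 42.9% | 1.07 |
| 0.90 | 0.70 | 0.36/0.78 = 46.2% | 1.15 |
| 0.90 | 0.50 | 0.36/0.66 = 54.5% | 1.36 |
| 0.70 | 0.80 | 0.28/0.76 = 36.8% | 0.92 |

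The last row shows the reversal if non-adherent women return more often. If SOC women were selected with the same a and b, both arms would show the same share and RR would be 1.00 in every row. If the SOC rule is read as study visits, the comparator is empty and no RR exists.

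**4. Shell against text**

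The Secondary Analysis 1 text supports the ITT block of Table 3. Nothing in it supports the per-protocol block, the aRR or the multivariable model in the title.

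**The case against.** The strongest reply is that the SAP never says the four-to-five-session rule applies at Week 4. The rule sits under Co-Primary Analysis 1, and Secondary Analysis 1 has no per-protocol step. Table 3 has the same layout as Tables 1 and 2, so the extra block may simply have been carried over. That is plausible. But it is the only rule the SAP offers, and if another was intended it is unwritten. On either reading the shell needs correcting.

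The reply also limits what can be claimed about bias. A reader might infer that the column would produce a false short-term benefit. For example, with 85% of adherent and 60% of non-adherent intervention women qualifying, the selected share is 0.34/0.70 = 48.6%, an RR of 1.21 from no effect. The documents do not support that as an expected result, for three reasons:

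- The rates are assumed. No figure in the protocol or SAP links Week 4 adherence to later attendance. Week 8 may be done by phone (Protocol 8.3.5), and women are followed whether or not they take PrEP (Protocol 8.3.8); both could weaken such a link.
- The calculation leaves SOC unrestricted, whereas the SAP restricts SOC too.
- Equal selection in both arms gives RR 1.00. Some difference between arms could remain, because schedules differ and reminders and missed-visit follow-up are for the intervention arm only (Protocol 8.4), but its size cannot be derived.

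A reader might also infer that a Week 4 rule based on the Enrollment and Week 2 sessions would rescue the column. It would end selection on the future. But the Week 2 visit exists only in the intervention arm (Protocol 8.3.3), so intervention women would be selected on a step with no SOC counterpart.

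Finally, the ITT estimate is printed alongside and is labelled the primary analysis for this objective. That limits the harm but does not justify the extra column.

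**Conclusion.** The point holds as an inconsistency between shell and text with a timing flaw behind it. The Table 3 per-protocol estimate has no planned analysis to fill it. Under the SAP's only rule it would be either selected on attendance after the outcome or not computable.

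The session counts come directly from the schedule: three of five intervention sessions by Week 4, six qualifying patterns of 32, all reaching past Week 4. The finding of no qualifying SOC participant rests on reading SOC sessions as scheduled study visits. The direction and size of any bias are unknown, and the RRs above show only that it could go either way.

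The effect is confined to a supportive column for a secondary endpoint. No co-primary result or sample-size figure changes. The SOC half of the rule also bears on the Week 12 per-protocol tables, which the correction below does not address.

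**What to change.** In SAP Appendix Table 3, delete the per-protocol block with its aRR, confidence interval and p-value, and remove the word multivariable from the title. The shell then shows the single ITT RR that the Secondary Analysis 1 text plans. Do not substitute a rule based on the Enrollment and Week 2 sessions, for the reason given above.

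The cost is an edit to one table shell. Trial conduct, data collection, the co-primary analyses and the Secondary Analysis 1 text stay as they are.
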